
Target Accrual and Study Duration
	
Phase I: A maximum of 18 participants will be enrolled to the non-randomized dose escalation portion of this study. The number of participants required is a function of the unknown dose-toxicity relationship.
 
Phase II: A maximum of 99 participants will be enrolled to the randomized Phase 2 portion of this study (excluding patients replaced due to ineligibility or inability to start therapy).
 
Participants will be enrolled from up to 4 sites including Roswell Park.
 
This study is anticipated to complete accrual within 4 years of study activation. Patients will receive either nintedanib or placebo to be administered for 6 months. Patients will be followed for at least one year for initial primary analysis of study outcomes. Patients will be followed for no longer than 2.5 years.

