
Study Procedures
	
Physical Examination: Baseline, Cycle 1 Day 1, Cycle 2 through Cycle 6 Day 1, anytime when radiation pneumonitis is suspected to have occurred (within the first 6 months after completing radiation therapy), end of active treatment, between 76 to 97 days after last nintedanib/placebo dose, between 166 to 187 days after last nintedanib/placebo dose, long term follow-up.
 
Hematology: Baseline, Cycle 1 Day 1, Cycle 2 through Cycle 6 Day 1, anytime when radiation pneumonitis is suspected to have occurred (within the first 6 months after completing radiation therapy), end of active treatment, between 166 to 187 days after last nintedanib/placebo dose, long term follow-up.
 
Chemistry: Baseline, Cycle 1 Day 1, Cycle 2 through Cycle 6 Day 1, anytime when radiation pneumonitis is suspected to have occurred (within the first 6 months after completing radiation therapy), end of active treatment, between 166 to 187 days after last nintedanib/placebo dose, long term follow-up.
 
Disease Evaluation: Baseline, Cycle 3 Day 1, Cycle 6 Day 1, anytime when radiation pneumonitis is suspected to have occurred (within the first 6 months after completing radiation therapy), between 76 to 97 days after last nintedanib dose, between 166 to 187 days after last nintedanib/placebo dose, and long term follow-up.
 
Performance Status: Baseline, Cycle 1 Day 1, Cycle 2 through Cycle 6 Day 1, anytime when radiation pneumonitis is suspected to have occurred (within the first 6 months after completing radiation therapy), end of active treatment, between 76 to 97 days after last nintedanib/placebo dose, between 166 to 187 days after last nintedanib/placebo dose, long term follow-up.
 
Adverse Events: Baseline, Cycle 1 Day 1, Cycle 2 through Cycle 6 Day 1, anytime when radiation pneumonitis is suspected to have occurred (within the first 6 months after completing radiation therapy), end of active treatment, between 76 to 97 days after last nintedanib/placebo dose, between 166 to

	187 days after last nintedanib/placebo dose, long term follow-up.

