Statistical Analysis	
Sample Size Determination: A maximum of 18 participants will be enrolled to the non-randomized dose escalation portion of this study. The number of participants required is a function of the unknown dose-toxicity relationship.
 
A maximum of 99 participants will be enrolled to the randomized Phase 2 portion of this study (excluding patients replaced due to ineligibility or inability to start therapy).
 
Participants will be enrolled from up to 4 sites including Roswell Park. Accrual is expected to take 4 years.
 
Phase II Randomization: Patients will be randomized to either the placebo or nintedanib arm in a 1:2 fashion using a stratified permuted block randomization scheme. The randomization lists to be used in this study will be generated by the study biostatistician. Patients will be included in data analyses according to their randomized treatment assignment irrespective of the treatment actually received (intent-to-treat). After randomization, initiation of the study intervention will take place once symptoms arise for the patient, this will be left to the patient's discretion. Patient randomization will be done by the Department of Biostatistics at Roswell Park.

INVESTIGATOR STUDY ELIGIBILITY VERIFICATION FORM

Participant Name: (Network sites use participant initials): _____

Medical Record No.: (Network sites use participant ID): _____

Title: A Phase II Randomized, Double-Blind, Placebo-Controlled Study Evaluating Nintedanib versus Placebo as Prophylaxis against Radiation Pneumonitis in Patients with Unresectable NSCLC Undergoing Chemoradiation Therapy

INCLUSION CRITERIA				
Yes	No	N/A	All answers must be "Yes" or "N/A" for participant enrollment.	Date
			1. Age 18 years or greater.	
			2. Histologically or cytologically-proven non squamous cell NSCLC. Mixed histology with SCLC component not allowed.	

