			1. WBRT < 14 days from the anticipated start of nintedanib/placebo administration.	
			2. Squamous cell NSCLC	
			3. Unable to start nintedanib/placebo treatment between 4 - 8 weeks after completing the last dose of thoracic radiation.	
			4. Active untreated brain or leptomeningeal metastases. In patients with treated CNS metastases, eligible if symptoms controlled for at least 4 weeks. Dexamethasone allowed if total daily dose does not exceed 2 mg.	
			5. Major injuries or surgery (e.g., craniotomy) < 28 days from the start of nintedanib/placebo administration. Wound should be healed prior to starting therapy.	
			6. Second malignancies are allowed as long as the disease does not require active treatment with concomitant systemic cytotoxic chemotherapy, investigational or biologic therapy (e.g., anti-CTLA4 or HER2 monoclonal antibodies). Hormone-related therapies (e.g., LHRH agonists, tamoxifen, etc.) are allowed.	
			7. Concurrent uncontrolled illness including, but not limited to, ongoing or active infection, symptomatic congestive heart failure, unstable angina pectoris, cardiac arrhythmia, or psychiatric illness/social situation that would increase the risk associated with study participation and/or limit compliance with study requirements.	
			8. Inability to swallow study medication.	
			9. Presence of active malabsorption disorder (e.g., flare episodes documented within the preceding 3 months, presence of symptoms requiring daily medications for control) or history of extensive small bowel resection.	
			10. Known bleeding or thrombotic diathesis.	

EXCLUSION CRITERIA				
Yes	No	N/A	All answers must be "No" or "N/A" for participant enrollment.	Date

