2 RATIONALE

Nintedanib 200 mg orally twice daily had been evaluated in several Phase III NSCLC studies as discussed previously. Based on the data summarized in **Section 1.4**, the use of nintedanib may potentially mitigate both the early phase of inflammatory response and the latter phase of fibrotic response. Because the risk of acute radiation pneumonitis is greatest within the first 6 months after completion of thoracic radiation, this study will randomize patients to begin treatment

between 4 - 8 weeks upon completion of the last fraction of thoracic radiation, with either nintedanib or placebo treatment for 6 months.

Antiangiogenic treatment with the orally available triple angiokinase inhibitor nintedanib with inhibition of VEGFR, PDGFR and FGFR offers the chance to control both locally recurrent and distant metastatic disease on an outpatient basis. Treatment with nintedanib may have the potential to provide significant benefit to patients with locally advanced NSCLC by slowing tumor progression and metastasis, since its cellular target is expressed on the tumor vasculature in most malignancies. Induction of endothelial cell apoptosis may result in subsequent degradation of tumor vessels and subsequent tumor necrosis. Additionally, tumor growth may be affected by direct anti-tumor effects (e.g., tumor cells that express VEGFR, PDGFR or FGFR). Moreover, due to the positive effects of nintedanib therapy in patients with ILD, we hope that nintedanib therapy can also ameliorate radiation pneumonitis in locally advanced NSCLC who receive chemoradiation therapy.

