6.2 Exclusion Criteria

- 1 WBRT < 14 days from the anticipated start of nintedanib/placebo administration.
- 2 Squamous cell NSCLC

- 3 Unable to start nintedanib/placebo treatment between 4 – 8 weeks after completing the last dose of thoracic radiation.
- 4 Active untreated brain or leptomeningeal metastases. In patients with treated CNS metastases, eligible if symptoms controlled for at least 4 weeks. Dexamethasone allowed if total daily dose does not exceed 2 mg.
- 5 Major injuries or surgery (e.g., craniotomy) <28 days from the start of nintedanib/placebo administration. Wound should be healed prior to starting therapy.
- 6 Second malignancies are allowed as long as the disease does not require active treatment with concomitant systemic cytotoxic chemotherapy, investigational or biologic therapy (e.g., anti-CTLA4 or HER2 monoclonal antibodies). Hormone-related therapies (e.g., LHRH agonists, tamoxifen, etc.) are allowed.
- 7 Concurrent uncontrolled illness including, but not limited to, ongoing or active infection, symptomatic congestive heart failure, unstable angina pectoris, cardiac arrhythmia, or psychiatric illness/social situation that would increase the risk associated with study participation and/or limit compliance with study requirements.
- 8 Inability to swallow study medication.
- 9 Presence of active malabsorption disorder (e.g., flare episodes documented within the preceding 3 months, presence of symptoms requiring daily medications for control) or history of extensive small bowel resection.
- 10 Known bleeding or thrombotic diathesis.
- 11 History of arterial or venous thromboembolic event within 12 months prior to study participation.
- 12 Active hemoptysis or history of clinically relevant hemoptysis as determined by the treating physician. Patients who had history of transient minor hemoptysis after bronchoscopic biopsy are eligible unless deemed otherwise by the treating physician.
- 13 CTCAE Grade 2 or higher proteinuria.
- 14 Investigational agent administered < 28 days prior to treatment with nintedanib. Last dose of systemic chemotherapy administered < 14 days prior to treatment with nintedanib.
- 15 Known chronic active hepatitis B or hepatitis C. HIV-positive patients receiving or are candidates for antiretroviral therapy are also excluded.
- 16 Pregnancy or breast feeding. Female patients with child-bearing potential must have a negative pregnancy test (β -HCG test in urine or serum) prior to commencing study treatment.

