9.1 Participant Randomization and Registration

Phase I:

Subjects enrolled to the dose escalation portion of the study will NOT undergo randomization (i.e. not blinded to treatment) and will receive the active drug nintedanib according to the dose level assigned.

Phase II:

Patients will be randomized, by site, at the baseline visit into one of 2 arms, placebo or nintedanib, in a 1:2 fashion using a block-permutation design, but this will be masked to the investigator and patient. The randomization list will be generated by the study biostatistician.

Patients will be included in data analyses according to their randomized treatment assignment irrespective of the treatment actually received (intent-to-treat).

Patients will be assigned a study number in the order of randomization.

No study-specific procedures are to be performed until informed consent is obtained. Eligibility of each patient will be established prior to study enrollment.

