13.3 Randomization

Phase II: Patients will be randomized to either the placebo or nintedanib arm in a 1:2 fashion using a stratified permuted block randomization scheme. The randomization lists to be used in this study will be generated by the study biostatistician. Patients will be included in data analyses according to their randomized treatment assignment irrespective of the treatment actually received (intent-to-treat). After randomization, initiation of the study intervention will take place within the timeframe specified in the eligibility period. Patient randomization will be done electronically by the Department of Biostatistics at RPCI.

The activity of the dose escalation patients receiving durvalumab will not hold enrollment for patients not exposed to immunotherapy agents. (i.e. patients can enroll to Phase II ahead of dose

escalation if the choice is not to give durvalumab. If patient is going to receive durvalumab, it is required to go through dose escalation first until MTD is determined).

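### The synopsis starts study drug when symptoms arise, as the patient chooses; Section 13.3, with exclusion 3 and the Rationale, ties the start to 4–8 weeks after thoracic radiation

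*Combined protocol and SAP*

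**What the plan says.** The synopsis, under Statistical Analysis (Phase II Randomization), sets out 1:2 allocation in stratified permuted blocks and analysis as randomized. It then fixes the moment of first treatment: "initiation of the study intervention will take place once symptoms arise for the patient, this will be left to the" discretion of the patient. It does not say which symptoms count.

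Section 13.3 (Randomization) repeats that paragraph almost item for item. At the same point it says that "initiation of the study intervention will take place within the timeframe specified in the eligibility period". Section 13.3 gives no number of weeks. The number comes from two other places:

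- Exclusion 3 on the Eligibility Verification Form reads "Unable to start nintedanib/placebo treatment between 4 - 8 weeks after completing the last dose of thoracic radiation". Section 6.2 carries the same criterion.
- Section 2 (Rationale) has patients begin treatment "between 4 - 8 weeks upon completion of the last fraction of thoracic radiation".

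Elsewhere the synopsis describes treatment without any symptom condition: "Patients will receive either nintedanib or placebo to be administered for 6 months" (Target Accrual and Study Duration). Section 9.1 places randomization early: "Patients will be randomized, by site, at the baseline visit into one of 2 arms".

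**The concern.** The title and Section 5 present the trial as one of prophylaxis. Section 13.5 makes the primary outcome a yes/no variable: symptomatic radiation pneumonitis of Grade 2 or above, six months after chemoradiation ends. A start rule triggered by symptoms therefore touches the outcome itself. If the synopsis means pneumonitis symptoms, it makes the onset of what the trial tries to prevent the signal to begin prevention.

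The start rule also defines what the two arms are. Analysis as randomized compares two treatment policies, and here the text describes two different ones. One treats every randomized patient from a fixed period after radiation. The other treats only patients who develop symptoms and choose to start. The randomized part allows up to 99 patients at up to 4 sites, and all of them need a single rule.

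**Working it through.** No sample size, power or event count enters this point, so there is no figure of the plan to reproduce. The check is a comparison of texts.

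**1. The start rules side by side**

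| Place | What starts treatment | Who or what decides |
|---|---|---|
| Synopsis, Phase II Randomization | Onset of undefined symptoms | The patient |
| Section 13.3 | Timeframe set by eligibility | Calendar |
| Exclusion 3 (form and Section 6.2) | Ability to start 4–8 weeks after last thoracic radiation | Calendar, as an entry criterion |
| Section 2 | 4–8 weeks after last fraction | Calendar |

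**2. Same patients, same act?** Yes. The synopsis paragraph and Section 13.3 both concern randomized Phase II patients and both describe the first step after randomization. The difference cannot be explained by two populations or two treatments.

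**3. Which timeframe does Section 13.3 point to?** Only exclusion 3 sets a period for starting nintedanib or placebo relative to radiation. Inclusion 4 also mentions weeks after radiation (4–6), but it concerns tumour response. Exclusions 1, 5 and 14 set minimum gaps from other treatments or surgery, not a start window.

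**4. Can both rules be met?** Only in a patient whose symptoms arise, and who chooses to start, in time for a first dose by week 8. For a patient whose symptoms come later, the synopsis and Section 13.3 give different start dates. For a patient who never has symptoms, Section 13.3 gives a start date and the synopsis gives none.

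**5. Does the visit structure fit the synopsis clause?**

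- Randomization is at the baseline visit (Section 9.1), and baseline evaluations fall within 4 weeks before the first dose (Section 9.2). The first dose is therefore planned within about 4 weeks of randomization. Waiting for symptoms has no such limit.
- Dispensing is listed at Cycle 1 Day 1 (Section 9.3) and on Day 1 of Cycles 2 to 6 (Section 9.4). Table 5 agrees.
- The visit for suspected pneumonitis (Section 9.5) lists no dispensing.
- The synopsis's own Study Procedures list that visit as separate from the first treatment visit: "Baseline, Cycle 1 Day 1, Cycle 2 through Cycle 6 Day 1, anytime when radiation pneumonitis is suspected to have occurred".

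The clause does not fit this structure, and no other section makes the start depend on symptoms or on the patient's choice.

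**6. What would follow for the primary outcome?** Assume that pneumonitis symptoms are meant and that the clause is followed.

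- A patient with symptoms may already have a Grade 2 event at the first dose. Study drug could not have prevented it.
- A patient without symptoms takes neither nintedanib nor placebo, so the arms do not differ in treatment for that patient.
- Any difference between arms could then arise only from treatment begun after symptom onset. That is not a test of prophylaxis.

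If other symptoms are meant, the documents do not say which, and the consequence cannot be traced.

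**The case against.** The strongest reply is that this is one sentence in a synopsis and that the rest of the protocol agrees on another course. Investigators sign an eligibility form carrying exclusion 3, drug is dispensed at a scheduled first visit, and Sections 2 and 13.3 use the calendar. It is reasonable to suspect leftover text that no site would act on. Much of this stands: the reach is narrow, and the documents record no symptom-triggered start. But the sentence is current text, not part of a log of changes, and it sits just ahead of the eligibility form that it conflicts with. That it is a leftover is an inference; the documents do not say so.

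A reader might also infer more than the documents support:

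- *That a later start breaches exclusion 3.* That criterion concerns ability to start and applies at entry. A patient who could have started in time but started later departs from Section 13.3, and has not clearly met an exclusion.
- *That the size can be read from the calendar.* Six months is about 26.1 weeks. From week 4 that leaves 26.1 − 4 = 22.1 weeks, and from week 8 it leaves 26.1 − 8 = 18.1 weeks, so 18.1/22.1 = 82% of the interval lies after the window closes. This is a share of time. The documents give no distribution of symptom onset, so it says nothing about the share of patients or events affected.
- *That Section 7.2 adds a third rule.* It lets durvalumab patients start at any time once the MTD is known, but explains this as durvalumab doses possibly coming first, and still requires the other entry criteria. It gives no support to a symptom trigger.

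**Conclusion.** The contradiction holds. The current text gives two incompatible rules for when randomized Phase II patients begin study drug, and the visit schedule does not fit the one in the synopsis. It should be fixed, because a literal reading of the synopsis would change the question that the primary analysis answers.

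That consequence rests on two assumptions: that the undefined symptoms are those of pneumonitis, and that someone followed the clause. The documents establish neither. Its effect on the primary result cannot be quantified from them, and no loss of power is claimed. A reader might infer that patients were treated late or that data are compromised; nothing in the documents shows this.

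A reader might also infer, from the number of sections on the other side, that the synopsis is the text in error. This review takes no position on which rule is right. It says only that both cannot stand.

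**What to change.** Reconcile the synopsis paragraph with Section 13.3, exclusion 3 (on the form and in Section 6.2) and Section 2, so that one start rule stands throughout, and check that the visit schedule fits it. If any symptom condition is kept, define the symptoms. Tell sites the reconciled text. If patients have already been randomized, compare recorded start dates with it and document departures.

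The cost is small: a wording change at the next amendment, a notice to sites and, where it applies, a check of dates already collected. How many sections need editing depends on which rule the sponsor confirms.

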1 BACKGROUND

1.1 Study Disease

Lung cancer is the leading cause of cancer-related mortality in the United States and worldwide (1). Majority of patients present with an advanced unresectable stage of disease. Concurrent chemoradiation therapy is the standard of care in patients with Stage III locally advanced non-small cell lung cancer (NSCLC) (2). Symptomatic radiation pneumonitis occurs in 15 - 40% of NSCLC patients receiving concurrent chemoradiation (3,4). This treatment complication adversely affects quality of life and may rarely be fatal (3,4).

Various treatment-related risk factors have been identified that can predict the development of symptomatic radiation pneumonitis (4,5). These include V20 (lung volume receiving > 20 Gy), chemotherapy regimen and mean lung dose (MLD). For example, to limit the frequency of symptomatic radiation pneumonitis to < 30%, the V20 and MLD thresholds as calculated from the dose-volume histogram minus the gross tumor volume were 41.5% and 22.4 Gy, respectively (5). The use of carboplatin and paclitaxel regimen was associated with the highest risk in patients greater than 65 years (4).

The pathophysiology of radiation pneumonitis and the eventual pulmonary fibrosis that ensues is thought to be secondary to inflammatory and/or profibrotic cytokines such as IL-1 α , IL-6, IL-10 and TGF- β that are activated by volatile reactive oxygen and nitrogen species which are generated in response to the oxidative stress caused by the tissue damage incurred from radiation (6-10). A TH2-like immune response with elevated mRNA levels of the transcription factor GATA-3 has been implicated as well in this process (11). Pharmacologic inhibition of CC chemokine receptor 1 (CCR1) prevented lung inflammation and fibrosis induced by radiation (12). More recently, murine models of radiation-pneumonitis reveals early accumulation of CD4+FoxP3+Treg cells 21 days post-radiation. However, the role of these Treg cells in dampening or worsening radiation-induced inflammatory tissue damage is speculative at this time and not clearly defined (13).

Preclinical studies suggest that antioxidants can be effective radioprotectors in mice models (10, 13-14), but optimal dose and method of administration maybe challenging (15,16). Amifostine, a widely studied radioprotective agent metabolized to an active form which binds to free radicals, did not appear to reduce the incidence of pulmonary toxicity in the large RTOG 9801 Phase III trial in patients with locally advanced NSCLC receiving hyperfractionated radiation concurrently with chemotherapy, with no difference seen in the patient-reported quality of life (QOL) scales in terms of dyspnea, cough and chest pain between the amifostine versus no-amifostine groups (17,18).

